3.7.1.1 Vitamin K antagonist usage (e.g., Warfarin, Coumarins)

Clinical studies have shown a potentiation of the anticoagulant effect during concomitant administration of rosuvastatin and a vitamin K antagonist. Interactions of this type may be

clinically managed by close monitoring of the anticoagulant effect (expressed as International Normalised Ratio, INR).

For these reasons, careful monitoring of INR is required and investigators should, in accordance with usual practice, measure INR frequently until vitamin K antagonist dose stabilisation is achieved, and periodically thereafter, particularly in the following situations:

- when starting vitamin K antagonist therapy in a patient currently receiving study medication
- when a patient currently receiving a vitamin K antagonist begins study medication

In order that up-to-date information and advice can be provided, investigators must telephone their study monitor to discuss the situation with the relevant AstraZeneca Study Team Physician or the physician's delegate.

3.8 Treatment compliance

Patients will be asked to return all unused medication and bottles. The number of tablets issued minus the number of tablets returned will be used to calculate the number of tablets taken. From this information compliance will be calculated:

Compliance = (number of tablets dispensed-number of tablets return) x100Number of days between visit 2.1 and 3

Compliance will be checked at visit 3. For compliance patient should take more than 80% and less than 120% of the prescribed study medication.

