3.4.2 Doses and treatment regimen

AstraZeneca will provide centres with blinded supplies of study medication. Medication will be dispensed on visit 2.1 on which patients will be given two bottles. Each bottle will contain sufficient tablets and overage to finish study period (see Table 3).

At Visit 2.1 (week 0) following confirmation of eligibility, patients will be randomised to one of three treatment groups; rosuvastatin 10 mg, rosuvastatin 20 mg or placebo. Patients should take two tablets per day at the same day hour during 8 weeks (aprox 2 months). All study medication will be taken orally, with water if required, at any time of day or night.

Table 3Visit schedule

Dispensing Visit	Number of weeks	Number of bottles	Number of tablets per bottle
2.1	8	2	100 (56 days treatment, 2 tablets per day + 44 days overage)

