3.6 Blinding and Dummy methods and procedures for unbinding the study

3.6.1 Methods for ensuring blinding

The study employs a double blind, double dummy design. Medication for each treatment group will be supplied in identical bottles and will be labelled appropriately so as to maintain the study blind. Patients will receive 2 bottles, and should have on tablet of each bottle as a single dose a day. Patients will receive medication as follows:

- a) For rosuvastatin 10 mg/day treatment arm: 1 bottle of rosuvastatin 10 mg + 1 bottle of placebo, matching rosuvastatin 20 mg.
- b) For rosuvastatin 20 mg/day treatment arm: 1 bottle of rosuvastatin 20 mg + 1 bottle of placebo, matching rosuvastatin 10 mg.

c) For placebo treatment arm: 1 bottles of placebo matching rosuvastatin 10 mg + 1 bottle of placebo, matching rosuvastatin 20 mg.

All study personnel will be unaware of the randomised treatment until all decisions on the evaluability of the data from all patients have been made and documented.

Lipid profile results on visit 1 and 2 will be available for the investigator to made eligibility criteria.

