6.3 Description of analysis sets

Efficacy

Efficacy data will be evaluated based on the intention-to-treat (ITT) and per-protocol (PP) populations.

The ITT population will consist of randomised patients who have a baseline reading and at least one post-baseline reading for at least one efficacy variable, and who have taken at least one dose of study medication. The PP population will consist of all patients in the ITT population who did not have a major protocol violation or deviations that would be likely to affect the efficacy outcomes (i.e. patients taking lipid lowering therapy other tan study drugs).

Patients will be evaluated using randomised treatment/dose (i.e., rosuvastatin 10 mg, rosuvastatin 20 mg, or placebo) for the ITT efficacy analyses, and actual treatment/dose received for the PP efficacy analyses.

For the test of superiority (versus baseline), the ITT population is the primary analysis population. Analyses of the ITT population will be performed using the last observation carried forward (LOCF) method and also using observed data. The LOCF analysis is the primary analysis. LOCF is defined as the last non-missing post-baseline value for a variable carried forward. If no non-missing value exists after baseline, the value will be treated as missing in the analysis. The analyses will be repeated for the PP population as a robustness check using only observed data. Any differences in interpretation of the results from the ITT population will be explored. For tests of no clinically significant deterioration from baseline the ITT and PP populations will be considered equally important.

Safety

The randomised safety population will consist of all patients who were randomised and took at least 1 dose of study medication. Safety data will be evaluated using actual treatment/dose received. In addition safety data from the lead-in period will be evaluated for all patients who enter the lead-in period.

The safety, ITT, and PP populations (including violations and deviations) will be determined prior to treatment unblinding.

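### The compliance formula in Section 3.8 divides tablets taken by days, although two tablets a day are prescribed, so as worded full adherence scores 200%

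*Protocol*

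**What the plan says.** Protocol Section 3.8 first defines the numerator: "The number of tablets issued minus the number of tablets returned will be used to calculate the number of tablets taken". It asks for everything back: "Patients will be asked to return all unused medication and bottles". The formula then follows as "number of tablets dispensed-number of tablets return) x100Number of days between visit 2.1 and 3". The line that separates numerator from denominator did not survive extraction, but the words of both parts did, and neither contains a factor for tablets per day. The acceptance criterion closes the section: "For compliance patient should take more than 80% and less than 120% of the prescribed study medication". Compliance is checked once, at Visit 3.

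The regimen is stated elsewhere. Section 3.4.2 says "Patients should take two tablets per day at the same day hour during 8 weeks", and Section 3.6.1 says that patients "should have on tablet of each bottle as a single dose a day". Two bottles are dispensed at Visit 2.1, and Table 3 gives 100 tablets per bottle for a treatment period of 56 days.

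Section 6.3 builds the per-protocol population from ITT patients "who did not have a major protocol violation or deviations that would be likely to affect the efficacy outcomes". Its one example is use of other lipid-lowering therapy. It mentions neither the compliance score nor the 80-120% band.

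**The concern.** The criterion is a percentage of what was prescribed, so a patient who takes everything should score 100%. The formula instead gives tablets per day times 100. The two agree only for a regimen of one tablet a day. In this double-dummy trial they differ by a factor of two.

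Two things are at stake. The first is the adherence that the trial reports, since this is the only compliance measure and threshold the protocol defines. The second is conditional: if the score is used to identify major deviations, it decides who stays in the per-protocol set, which Section 6.3 uses as the robustness check on the primary result.

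**Working it through.** **Inputs**
- Tablets dispensed: 2 bottles x 100 = 200 (Section 3.4.2, Table 3).
- Prescribed: 2 tablets a day, one per bottle (Sections 3.4.2 and 3.6.1).
- Treatment period: 56 days (Table 3).
- Band: above 80% and below 120% (Section 3.8).

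**The plan's own supply figure.** Table 3 allots each 100-tablet bottle 56 days of treatment plus 44 days of overage. At one tablet per bottle per day, 56 + 44 = 100, so the figure reproduces. At two tablets a day from one bottle, 100/2 = 50 days, which would not cover 56. The supply is therefore reckoned at one tablet from each bottle per day, or two in total. Prescribed tablets over the period are 2 x 56 = 112.

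**Score as worded, pooled over both bottles:** (dispensed - returned) x 100 / days.

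**Score against tablets prescribed:** (dispensed - returned) x 100 / (2 x days).

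| True adherence | Tablets taken | Returned of 200 | As worded | Divided by 2 x days |
|---|---|---|---|---|
| 100% | 112 | 88 | 200% | 100% |
| 90% | 100.8 | 99.2 | 180% | 90% |
| 80% | 89.6 | 110.4 | 160% | 80% |
| 60% | 67.2 | 132.8 | 120% | 60% |
| 50% | 56 | 144 | 100% | 50% |
| 40% | 44.8 | 155.2 | 80% | 40% |

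**What the band admits.** As worded, 80-120% corresponds to 0.8 x 56 = 44.8 up to 1.2 x 56 = 67.2 tablets. Relative to 112 these are 40% and 60%. With prescribed tablets in the denominator, the band runs from 0.8 x 112 = 89.6 to 1.2 x 112 = 134.4 tablets.

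**Visit timing.** Windows of 2 days at Visit 2.1 and 3 days at Visit 3 let the interval run from 56 - 5 = 51 to 56 + 5 = 61 days. For d days of full adherence the score is 2d x 100/d = 200% whatever d is, so timing does not explain the discrepancy.

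**One bottle skipped.** A patient who takes all of one bottle's doses and none of the other's takes 56 tablets. As worded the score is 56 x 100/56 = 100%, a pass. In an active arm the bottle taken could be the placebo-matching one. With 2 x days the score is 56 x 100/112 = 50%, a fail.

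**Per-bottle reading.** Applied to one bottle alone, the formula gives (100 - 44) x 100/56 = 100% for full adherence. This is the only reading tried under which the formula works.

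**The case against.** The strongest defence is that a per-bottle calculation was intended. Table 3 reckons supply bottle by bottle, Section 3.6.1 assigns one tablet from each bottle per day, and on that basis the formula is correct. The criterion in words is also sound: 112 of 112 tablets is 100% of what was prescribed, so the sentence that sets the band does not itself reject adherent patients. Both points stand as far as they go. But Section 3.8 never says that the formula is applied per bottle, and its wording, with tablets issued less tablets returned and all unused medication and bottles brought back, points to a single pooled count. A sound criterion beside a formula that does not compute it is a contradiction within the section.

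The second line of defence concerns consequences, and most of it stands. The primary analysis is LOCF on the ITT population, which requires a single dose and no compliance score. Section 3.3.5.1 leaves severe non-compliance to the judgement of the investigator or sponsor, with no computed cut-off. Tablets returned are counted, so the score can be recomputed without loss of data.

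A reader might infer that the per-protocol set will hold the wrong patients and that its effect estimate will be diluted. The protocol does not support this, because Section 6.3 does not make the band a per-protocol criterion. Even if it did, the literal rule would exclude every patient at 60% true adherence or above. If most patients take more than that, the set would come out almost empty. Such a failure would be hard to miss when the populations are settled, which Section 6.3 requires before unblinding.

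A reader might also conclude that each bottle must separately fall within 80-120%. That would be a new acceptance criterion. The arithmetic error does not call for it, and the patient who skips a whole bottle already fails once the denominator is corrected.

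**Conclusion.** The formula is wrong as written. Pooled over both bottles, it doubles every patient's adherence: full adherence scores 200%, half scores 100%, and the 80-120% band selects 40-60% true adherence. This follows from the protocol's own figures and does not depend on visit timing. It rests on the pooled reading, which the wording favours. If a per-bottle calculation was meant, the arithmetic is right but the text omits the instruction that makes it so, and Section 3.8 still needs a correction.

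Reported adherence is wrong whenever the formula is applied as worded. The effect on the per-protocol set depends on non-compliance by this rule being treated as a major deviation, which the protocol does not state. The primary result is not touched. This should be fixed, but it does not threaten the trial's main conclusion. The statistical analysis plan was not available, and it may define the variable differently.

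**What to change.** Change the denominator in Section 3.8 to the tablets prescribed: 100 x (tablets dispensed - tablets returned) / (2 x days between Visits 2.1 and 3). The existing 80-120% criterion then means what it says and needs no change.

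Alternatively, keep days as the denominator and state that the formula is applied to each bottle separately. This gives two percentages per patient, so the text must also say how the criterion is read when there are two. The first option avoids that question.

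Reporting tablet counts by bottle is an optional addition. It would show which bottle was missed, provided that returns are recorded by bottle; the protocol mentions only tablet counts.

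The cost is one line in the protocol, carried through to wherever the score is derived. No new data, visits or procedures are needed. The correction should be made before the analysis populations are fixed.

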4. MEASUREMENTS OF STUDY VARIABLES

4.1 **Primary variable**

The primary variable is the change TG from baseline to week 8.

4.2 Secondary variables

Secondary variables are: non-HDL-C; LDL-C; TC; HDL-C; ApoA1; ApoB levels; ApoB/ApoA1; non-HDL-C/HDL-C; LDL-C/HDL-C; TC/HDL-C and hsCRP.

4.3 Screening and demographic measurements

The following screening and demographic data will be collected in the CRF:

- Date of birth, sex and race
- Significant medical and surgical history

- Prior and concomitant medication
- Height, weight, waist circumference, vital signs and physical examination

Patient-Reported Outcomes (PROs) (Not applicable) 4.4

- 4.5 Health Economic measurements and variables (Not applicable)
- 4.6 Pharmacokinetic measurements and variables (Not applicable)

4.7 Efficacy and pharmacodynamic measurement and variables

The efficacy variables for the study are described in the table below:

Table 5	Efficacy variable(s)
Objective	Variable(s)
Primary	Percentage change in TG levels from baseline to week 8.
Secondary	
1st	Percentage change in non-HDL-C levels from baseline to week 8.
2nd	Percentage change in lipids and lipoproteins (different to TG and non-HDL-C) from baseline to week 8 (LDL-C, TC, HDL-C, ApoA1, ApoB, TC/HDL-C; LDL-C/HDL-C; nonHDL-C/HDL-C and ApoB/ApoA1 indexes)
3rd	Percent change of hsCRP from baseline to week 8.

T ce

4.7.1 **Triglycerides levels**

Triglycerides levels will be assessed from laboratory data.

4.7.1.1 Methods of assessment

Patients must fast for at least 12 hours and have been sitting for at least 5 minutes before blood samples are taken for lipid analysis. If a patient attends for one of these study visits without having fasted (from 12 hours before) then they must be asked to return within the visit windows for their fasting blood sample.

Fasting concentrations of TG will be determined at visit 1, 2 and 3.

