At the end of the 5-week lead-in period, during visit 2, a new TG analysis will be made and eligible patients (those with TG levels between \geq 200 mg/dl and <800 mg/dl on visit 2), will be randomised (on visit 2.1) with a 1:1:1 randomisation ratio to receive blinded treatment with either rosuvastatin 10 mg, rosuvastatin 20 mg or placebo. During the 8 weeks of the randomised treatment period, patients will continue with the TLC.

Clinical Study Protocol Drug Substance Rosuvastatin Study Code DM-CRESTOR-0002 Edition Number 2.1 Date 28-March-2007

End Points

– **Primary end point:**

1. Change (reduction) in triglycerides levels from baseline to end of treatment (week 8).

- Secondary end points:

- Change (reduction) in no-HDL-C from baseline to end of treatment,.
- Change in LDL-C; TC; ApoB; ApoA1; ApoB/ApoA1; TC/HDL-C; LDL-C/HDL-C, non-HDL-C/HDL-C index from baseline to the end of treatment.
- Change in hsCRP levels from baseline to the end of treatment.

Patient reported outcomes (PROs)

- There are no patient reported outcomes for this study

- Health economics

- There are no health economic evaluations in this study

– Pharmacokinetic

- There are no pharmacokinetic outcomes for this study

– Pharmacodynamic

- As stated in the protocol

– Safety

- Safety evaluation, as determined by the incidence and severity of adverse events and abnormal laboratory values
- Genetics
 - There are no genetics outcomes for this study

Statistical methods

Lipids and lipoproteins are: Triglycerides, no-HDL-C, LDL-C, total cholesterol, HDL-C, ApoA1, and ApoB levels and ApoB/ApoA1, no-HDL-C/HDL-C and LDL-C/HDL-C indexes. Baseline for calculating percent change in a lipid or lipoprotein will be the values from the randomization visit (visit 2.1).

The following analyses will be performed for TG:

- Last observation carried forward (LOCF) on the ITT (Intention to treat) population for primary and secondary endpoints at week 8. This will be the primary analysis.
- Observed data on the per Protocol (PP) population for primary and secondary endpoints at week 8.

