Visit window allowed is ± 2 day. During this visit, laboratory results of the prior visit will be available and patients fulfilling the inclusion criterion will be randomised.

- 1. Fasting TG \geq 200 mg/dL and < 800mg/dL from visit 2.
- 2. Fasting LDL-C \geq 100mg/dL and \leq 190 mg/dL at visit 2.
- 3. Record of adverse events
- 4. Study drug will be dispensed in this visit.
- 5. Record of concomitant medication

[figure not shown]
Visit 3. Final (Week 8)

Visit window allowed is ± 3 days. Visit 3 will occurred after 8 weeks of following patients with treatment. This will be the final visit.

- 1. TLC advisory
- 2. Complete physical examination including anthropometrics and vital signs
- 3. Laboratory samples (see table 1)
- 4. Record of adverse events
- 5. Record of concomitant medication
- 6. Study drug will be recovered in this visit. Tablets will be counted and noted for assessing compliance.
- 7. All patients will be offered the opportunity to continue with active commercially available therapy with rosuvastatin, according to the expert opinion of investigator, once the protocol is complete.

Clinical Study Protocol Drug Substance Rosuvastatin Study Code DM-CRESTOR-0002 Edition Number 2.1 Date 28-March-2007

Figure 1 Study flow chart

RSV: rosuvastatin

Clinical Study Protocol Drug Substance Rosuvastatin Study Code DM-CRESTOR-0002 Edition Number 2.1 Date 28-March-2007

Table 1 **Study Plan**

Week	-5	-1	0	8
Visit	1	2	2.1 ⁿ	3
Visit window		± 3 days	±2 day	± 3 days
Informed consent ^a	✓			
Dietary counselling	✓		✓	✓
24 hrs diet recall	✓		✓	✓
Medical history/demography	✓			
Concomitant medication	✓ b	✓	✓	✓
Physical examination ^c	✓ ^d	✓		✓
Vital signs	✓	✓		✓
Eligibility criteria ^e	✓	✓	✓	
Randomization			✓	
Fasting lipid profile ^f	✓	✓		✓
Apolipoproteins ^g		✓		✓
TSH	✓			
Glucose	✓	✓		✓
HbA _{1c}	✓			
Urinalysis ^h		✓		✓
Reduced hepatic profile ^j	✓			
Complete hepatic profile ^k		✓		✓
Urea	✓	✓		✓
Creatinine	✓	✓		✓
СК	✓	✓		✓
β-HCG ¹	✓			
hsCRP		✓		✓
Adverse events ^m		✓	✓	✓
Study drug dispensing			✓	
Study drug compliance and accountability				~

^a Informed consent will be taken at or before Visit 1, before any study related procedures are performed ^b Prior medications to be collected at Visit 1

^c Weight and waist circumference will be measured at Visits 1, 2 and 3. Height will additionally be measured at Visit 1

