3.3.2 Inclusion criteria

For inclusion in the study lead-in period at Visit 1, patients must fulfil all of the following criteria:

- 1. Provision of written informed consent
- 2. Male or female aged ≥ 18 years
- 3. Statin naïve patients (as defined by protocol)
- 4. No previous lipid lowering treatment other than statins 6 months before visit 1
- 5. Fasting TG concentrations at visit 1 of: $\geq 200 \text{ mg/dL}$ and < 800 mg/dlL
- 6. Fasting LDL-C concentrations at visit 1 of: $\geq 100 \text{ mg/dL}$ and $\leq 190 \text{ mg/dL}$

(Note: the results of the above laboratory sample will not be available at visit 1 to make the eligibility decision. Therefore, if the subject's medical history meets the eligibility criteria the subject can enter into the dietary lead-in period of the study. However, when the laboratory results are available, if the results do not meet the above criteria, the subject should be contacted and discontinued from the study)

- 7. Fasting TG concentrations at visit 2 of: \geq 200 mg/dL and < 800 mg/dlL
- 8. Fasting LDL-C concentrations at visit 2 of: $\geq 100 \text{ mg/dL}$ and $\leq 190 \text{ mg/dL}$
- 9. Subjects willing to follow all study procedures including the attendance at clinics for scheduled study visits, fasting prior to clinic visits (Visits 1, 2 and 3 blood draws) and compliance with study treatment regimen.

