6.2 Description of outcome variables in relation to objectives and hypotheses

Each outcome variable relates to the corresponding objective as described in Section 4.7.

Primary efficacy outcome variable

1. Percentage change in TG levels from baseline to week 8.

Secondary efficacy outcome variables

- 1. Percentage change in non-HDL-C levels from baseline to week 8.
- 2. Percentage change in lipids and lipoproteins (different to TG and non-HDL-C) from baseline to week 8 (LDL-C, TC, HDL-C, ApoA1, ApoB, TC/HDL-C; LDL-C/HDL-C; nonHDL-C/HDL-C and ApoB/ApoA1 indexes).
- 3. Percent change of hsCRP from baseline to week 8.

Secondary safety outcome variables

1. Safety evaluation as determined by the incidence and severity of adverse events and abnormal laboratory values

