6.4 Method of statistical analysis

6.4.1 Efficacy

6.4.1.1 Triglycerides levels

The following analyses will be performed for TG:

- Last observation carried forward (LOCF) on the ITT (Intention to treat) population for primary and secondary endpoints at week 8. This will be the primary analysis.
- Observed data on the per Protocol (PP) population for primary and secondary endpoints at week 8.

Initially a Friedman analysis will be performed, then, for comparing each one of Rosuvastatin groups against placebo group at week 8 a U Man Whitney test will be done. Also, the percentage of reduction –week 8 minus basal- obtained in the placebo group will be contrasted against the percentage of reduction in each one of the Rosuvastatin groups using a U Man Whitney test. In all the cases a p < 0.05 will be considered significant.

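### The placebo comparison of TG uses one of two pre-randomisation readings and no covariate, so a modest, nearly free gain in precision is left out.

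*Protocol*

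**What the plan says.** Section 4.7.1.1 of the protocol fixes the sampling times: "Fasting concentrations of TG will be determined at visit 1, 2 and 3". Table 1 places these at weeks -5, -1 and 8. Section 3.3.2 makes both early readings conditions of entry ("Fasting TG concentrations at visit 1 of" and "Fasting TG concentrations at visit 2 of"), each with the range 200 to <800 mg/dL. Section 4.7.2.1 sends all samples to one central laboratory.

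The primary outcome variable in section 6.2 is "Percentage change in TG levels from baseline to week 8". The synopsis, under Statistical methods, takes the baseline from one visit: "Baseline for calculating percent change in a lipid or lipoprotein will be the values from the randomization visit", which it labels visit 2.1. Table 1 shows no blood draw at that visit, and section 3.1 says of it: "During this visit, laboratory results of the prior visit will be available and patients fulfilling the inclusion criterion will be randomised". The Visit 2 sample is therefore the only one that fits.

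Section 6.4.1.1 contains two Mann-Whitney comparisons with placebo. One uses week-8 levels and so no baseline at all. In the other, the percentage of reduction "obtained in the placebo group will be contrasted against the percentage of reduction in each one of the Rosuvastatin groups". Neither has a covariate. Section 6.4.1.2 carries the approach over to the other lipids.

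**The concern.** A percentage change from one reading carries the full within-patient variation of that reading, and fasting TG varies within a patient from one visit to the next. A second pre-randomisation reading tells us more about the patient's underlying level, even after adjustment for the first. Here it has already been collected, under the same fasting rule and in the same laboratory, for every correctly randomised patient.

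What is at stake is the width of the confidence interval for each dose against placebo, on TG and on the other lipids drawn at both visits. The size calculation in section 6.5 gives no protection, because it rests on two proportions and contains no SD of TG change.

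**Working it through.** **The plan's own figure.** Section 6.5 gives proportions 0.029 and 0.229, two-sided 5%, 90% power and 67 per arm. With mean proportion 0.129:

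- n = [1.96·√(2·0.129·0.871) + 1.2816·√(0.029·0.971 + 0.229·0.771)]² / 0.20² = (0.9291 + 0.5799)² / 0.04 = 56.9, so 57 without continuity correction.
- With correction: (56.9/4)·[1 + √(1 + 4/(56.9·0.20))]² = 66.5, so 67. The stated figure reproduces.
- Power at 100 per arm comes to 98.4% with the correction, against 97% stated.

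No variance of TG change enters, so this figure cannot show what baseline noise costs.

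**Inputs that must be assumed.** The documents give no TG variability. On the log scale, let τ be the between-patient SD, σ the within-patient SD, ω the SD of individual response to treatment, and δ the SD of the patient-specific shift between Visits 1 and 2.

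**Worked case.** Take τ = 0.4, σ = 0.25, ω = 0.2 and δ = 0, ignoring selection on TG.

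- Log change from Visit 2: 2σ² + ω² = 0.125 + 0.040 = 0.165.
- Week 8 adjusted for Visit 2: σ² + ω² + τ²σ²/(τ² + σ²) = 0.1025 + 0.0100/0.2225 = 0.1474.
- Week 8 adjusted for both: σ² + ω² + τ²σ²/(2τ² + σ²) = 0.1025 + 0.0100/0.3825 = 0.1286.
- Ratio, both against Visit 2 only: 0.1286/0.1474 = 0.87.
- Ratio, both against log change: 0.1286/0.165 = 0.78.

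**With selection.** Requiring 200 to <800 mg/dL at both visits narrows the spread between patients and shrinks the gain. Simulation with within-patient CV 25% and ω = 0.20 gives these ratios to adjustment for Visit 2 only:

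| δ | residual variance ratio | reduction |
|---|---|---|
| 0 | 0.909 | 9% |
| 0.15 | 0.936 | 6% |
| 0.30 | 0.971 | 3% |

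Over the wider grid of assumed SDs, the reduction from adding Visit 1 runs from about 0 to 18%, with no scenario in which variance rose. The two-covariate model has 3-25% less variance than log change from Visit 2 alone.

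**Why not average the two readings.** The variance ratio of log change, mean of two readings against Visit 2, is (1.5σ² + δ²/4 + ω²)/(2σ² + ω²). It is 0.75 at best (δ = ω = 0) and passes 1 once δ²/4 > 0.5σ², that is δ > 1.41σ. With CV 15% (σ² = ln 1.0225 = 0.02225), δ = 0.30 and ω = 0, it is (0.0334 + 0.0225)/0.0445 = 1.26. Simulations with selection also show averaging raising variance, by up to about 8%.

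**What it means for power.** Assume 95 evaluable per arm (285/3, from section 3.1) and an SD of 35 points for percentage change. The standard error is 35·√(2/95) = 5.08.

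- Difference of 15 points: 15/5.08 - 1.96 = 0.99, so power is 84.0%. With 10% less variance it is 87.6%. The number per arm for 90% power is 2·(1.96 + 1.2816)²·35²/15² = 114.4, so 115; it falls to 103.
- Difference of 20 points: 97.6% becomes 98.6%.

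**The case against.** The strongest reply is that nothing here is an error. A baseline taken after the lead-in is conventional, and section 3.2.1 justifies the lead-in as a way to a reliable baseline. An extra precision covariate is often left to the SAP, which section 6.1 promises before unblinding. The covariates also need a model that the protocol does not use. Part of this stands: the point is a refinement. But the synopsis and section 6.4.1.1 themselves fix a single baseline and an unadjusted test, so a change there is a change to what the protocol states.

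The two readings are not replicates, and this stands in full. Visit 1 precedes the diet advice. Section 3.7 has disallowed drugs stopped on entry, and Table 4 includes insulin, glitazones and systemic corticosteroids. Table 1, note d, provides for review and titration of antihypertensives at Visit 1. The shift from Visit 1 to Visit 2 can therefore differ between patients. That rules out averaging but not adjustment, since a fitted coefficient gives Visit 1 only the weight it earns.

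A reader might infer that averaging would be worth some 25-38% more patients. The documents do not support that: they give no variability, and such figures leave out varying shifts between the visits and varying response to treatment. Averaging would also give one primary variable two baselines, one for the placebo contrast and one for the within-arm change.

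Lastly, sections 6.3 and 6.5 name and power the test against baseline within each arm. The gain described here does not reach that test.

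**Conclusion.** The point holds as a modest loss of precision in the dose-versus-placebo comparison. Visit 1 TG is collected in every correctly randomised patient and used only for eligibility. Under assumed variability, adding it beside Visit 2 removes roughly 0-18% of residual variance. The benefit shrinks as response to treatment, or the change between Visits 1 and 2, varies more between patients. It matters little if the true difference from placebo is near 20 points.

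It would be wrong to infer that the planned comparison is biased. Randomisation balances both readings between the arms in expectation, with or without the covariate. Nor does the point show that 330 patients are too few, because the documents give no SD from which to judge that.

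**What to change.** In section 6.4.1.1, specify that week-8 TG on the log scale is compared between each rosuvastatin dose and placebo with log Visit 2 TG and log Visit 1 TG as covariates, or by a rank-based analysis with both as covariates. Apply the same in section 6.4.1.2 to the other lipids and ratios measured at both visits. ApoA-1, ApoB and hsCRP have no Visit 1 sample and are left out.

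Keep the Visit 2 sample alone as the baseline for percentage change and for the within-arm tests, and do not average the two visits. The synopsis label of visit 2.1 for that baseline needs to be reconciled with Table 1 at the same time.

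The cost is a short change of analysis wording before unblinding, one added covariate, and a model in place of the simple rank test. No new visit, sample or data item is needed.
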